Title: **Observational Study of Clinical Features and Outcome
of Interstitial Lung Disease with Anti-neutrophil
Cytoplasmic Antibody in Chinese Patients**

NCT number: **NCT04413149**

Date: **2020-6-20**

Background and Objectives

Anti-neutrophil cytoplasmic antibody (ANCA) is occasionally positive in patients with interstitial lung disease (ILD), including patients with a diagnosis of ANCA-associated vasculitis (AAV) and patients with isolated ANCA-positive idiopathic interstitial pneumonia (IIP). Their clinical and prognostic differences are not well known. The purpose of this study is to investigate the clinical features and long-term outcome of ANCA-positive ILD and assess the difference between microscopic polyangiitis (MPA) associated ILD and isolated ANCA-positive IIP.

Methods

Study Population

Interstitial lung disease patients with anti-neutrophil cytoplasmic antibody.

Criteria

Inclusion Criteria:

- Males and females
- Aged from 18 to 85 years with informed consent
- Have a diagnosis of ILD based on clinical symptoms and radiologic features, with or without histopathologic results
- Have available ANCA testing results during the first visit and follow-up period

Exclusion Criteria:

- Connective tissue disease associated ILD
- ILD induced by drug, environment, or occupational exposure
- Hypersensitivity pneumonitis and sarcoidosis

Group Information

In all the patients with ANCA-positive ILD, those who were diagnosed with MPA according to 2012 Chapel Hill consensus criteria are defined as **MPA-ILD group**,

and patients with isolated ANCA-positivity who did not fulfill the MPA criteria are classified as **ANCA-IIP group**

Data collection

Baseline information at the time of initial diagnosis was obtained and the following items were analyzed:

- demographics information (age, gender)
- clinical course
- clinical symptoms and signs
- laboratory findings (blood and urine routine, liver and renal function tests, erythrocyte sedimentation rate [ESR], C reactive protein [CRP])
- rheumatoid factor
- serologic autoantibodies [ANA, anti-ENA, ANCA, anti-CCP])
- pulmonary function tests (PFTs) (ventilation and diffusion capacity test)
- chest high-resolution computed tomography (HRCT)

ANCA was assessed by indirect immunofluorescence while MPO-ANCA and PR3-ANCA titers were measured by ELISA.

Chest HRCT images were evaluated together by more than two pulmonologists and radiologists blinded to clinical and histopathological information. The HRCT scans were analyzed for the following characteristics: ground-glass opacity, consolidation, reticular pattern, honeycombing, traction bronchiectasis, interlobular septal thickening, curved linear opacity, pleural thickening, etc.

The patients were followed up at least once a year and basic laboratory tests, serologic autoantibodies, PFT and chest HRCT were evaluated routinely. The follow-up period ended in April 2019 and the outcomes were defined as death from all causes and lung transplantation.

Statistical Analysis Plan

All data are analyzed using statistical analysis software (version 24.0, SPSS, IBM

Corporation). Normally distributed variables are presented as means \pm SD, and Student t test is used for comparisons. Continuous, non-normally distributed data are presented as median with interquartile ranges (IQR), and the Mann-Whitney U test is used for comparisons. Categorical variables are expressed as number (%), and χ^2 test or Fisher's exact test is used for comparisons. Survival analysis is performed by Kaplan-Meier analysis using log-rank test. Cox models are used to examine the association between baseline characteristics and mortality. *P* values are two-sided, and *P* $<$ 0.05 is considered statistically significant.

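### If inclusion needs an ANCA result in follow-up as well as at the first visit, early deaths drop out and Kaplan-Meier survival counted from diagnosis is too high

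*Combined protocol and SAP*

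**What the plan says.** Under Inclusion Criteria, patients must "Have available ANCA testing results during the first visit and follow-up period". The same list requires consent: "Aged from 18 to 85 years with informed consent". The Background and Objectives section sets out to "investigate the clinical features and long-term outcome of ANCA-positive ILD" and to compare MPA-ILD with isolated ANCA-positive IIP.

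Under Data collection, "Baseline information at the time of initial diagnosis was obtained", and ANCA is among the items listed at that point. For follow-up, "The patients were followed up at least once a year" and "serologic autoantibodies, PFT and chest HRCT were evaluated routinely". Follow-up closed in April 2019, and "the outcomes were defined as death from all causes and lung transplantation".

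In the Statistical Analysis Plan, "Survival analysis is performed by Kaplan-Meier analysis using log-rank test", and Cox models relate baseline characteristics to mortality. No section gives the time origin for these analyses, a landmark, delayed entry, or a rule for patients who die or are transplanted before a second ANCA test. The group definitions rest on ANCA positivity and the MPA criteria and do not call for a second test.

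**The concern.** On the conjunctive reading, eligibility depends on the future. A patient who dies before a follow-up ANCA test cannot qualify, nor can one who is transplanted and never tested again. Those are the study's outcome events. Patients who do qualify are credited with the interval between diagnosis and the qualifying test, during which they could not have died and remained in the cohort. Counted from diagnosis, that interval is immortal time.

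Long-term outcome is a stated objective, so the absolute survival curve matters in its own right. The group comparison is exposed too if early risk, or the timing or availability of repeat testing, differs between MPA-ILD and ANCA-IIP.

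**Working it through.** The plan states no sample size, event count, survival rate or power, so it has no figure to reproduce. The check is a conditional-survival calculation.

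**Inputs from the document.** A result at both times (Inclusion Criteria, conjunctive reading); time from diagnosis (inferred from the baseline definition in Data collection); visits yearly or more often, so a first follow-up test up to about 12 months out.

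**Assumed inputs.** Constant hazard; true 5-year survival S5 of 50%, 60% or 80%; qualifying test at L = 1/12, 0.25 or 1 year.

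**Direction.** If entry requires being alive at L and the clock starts at diagnosis, the curve estimates S(t)/S(L) for t > L and 100% for t ≤ L. Since S(L) ≤ 1, the result is never below S(t).

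**Formulas.** h = −ln(S5)/5; fraction excluded = 1 − exp(−hL); apparent S5 = S5/exp(−hL); share of 5-year deaths lost = fraction excluded/(1 − S5).

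**Worked case, S5 = 60%.** h = 0.5108/5 = 0.1022 per year. At L = 1, exp(−0.1022) = 0.9029, so 9.71% are excluded, apparent S5 = 0.60/0.9029 = 66.45%, and 9.71/40 = 24.3% of 5-year deaths are lost. At L = 0.25, 2.52% are excluded, apparent S5 is 61.55% and 6.3% of deaths are lost. At L = 1/12, the figures are 0.85%, 60.51% and 2.1%.

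**Apparent 5-year survival**

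| True S5 | Test at 1 month | 3 months | 12 months | Uniform on 3–12 months (simulated) |
|---|---|---|---|---|
| 50% | 50.58% | 51.76% | 57.43% | 54.5% |
| 60% | 60.51% | 61.55% | 66.45% | 63.9% |
| 80% | 80.30% | 80.90% | 83.65% | 82.3% |

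The last column comes from a simulation of 2,000,000 patients with individual test times; 8.3%, 6.2% and 2.7% are excluded, top to bottom. A separate simulation with random censoring and the same test times gave 64.0% with the follow-up-test condition and 60.0% without it, for a true 60%.

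**Group comparison, proportional hazards.** Two equal groups, reference hazard 0.102 per year, censoring at 5 years, test times uniform on 3–12 months in both. True hazard ratios of 1.0, 1.5 and 2.0 are estimated as 0.999, 1.502 and 2.005 in the selected cohort (full cohort 1.000, 1.500 and 2.004), with 15.4%, 16.3% and 17.3% of events lost.

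**Group comparison, non-proportional hazards.** Suppose first-year hazards of 0.30 and 0.10, then 0.10 in both groups, with every test at 1 year. True 5-year survival is exp(−0.30 − 0.40) = 49.7% against exp(−0.10 − 0.40) = 60.7%. The selected cohort shows exp(−0.40) = 67.0% in both, so the difference disappears. This shows what is possible; nothing in the documents indicates that it occurred.

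**The case against.** The strongest reply is that the bias needs two premises the document does not confirm. The criterion can be read as one span, so that a result at any time in it suffices. And the baseline sentence describes data collection, not the start of the survival clock. Context gives the milder reading some support: ANCA is already collected at diagnosis, the groups need no second test, no stated analysis uses a follow-up ANCA result, and no patient is reported as excluded on this ground.

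The size is also open. The 12-month column needs every qualifying test at the longest permitted interval, and tests at 1 to 3 months give only 0.3 to 1.8 points. Assuming, for scale, 100 patients, 60% survival and no censoring, the standard error is √(0.6 × 0.4/100) = 4.9 points. Finally, follow-up had closed before the document's date of June 2020, so rewording cannot undo a selection already made.

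All of this stands as a limit on the claim: a realised bias is not shown. It does not make the criterion adequate. Two readers could build different cohorts from it, and one of those cohorts selects on the outcome. The milder reading has its own gap: a patient first positive during follow-up but counted from diagnosis also carries immortal time. That past selection cannot be undone by wording is a reason to re-query the records and report the exclusions.

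**Conclusion.** The concern holds, conditionally. If a result was required at both times and time runs from diagnosis, the upward direction of the bias in absolute survival is certain and only its size is unknown. For assumed true 5-year survival of 50% to 80% under a constant hazard, the overstatement is 0.3 to 0.6 points with a 1-month test, 0.9 to 1.8 at 3 months, 3.7 to 7.4 at 12 months, and 2.3 to 4.5 with tests spread over 3 to 12 months.

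The log-rank and Cox group comparison mainly loses events. It is materially biased only if hazards are non-proportional, or if test timing or availability differs by group or prognosis; the documents neither show nor exclude either. If any result in the span suffices, the remaining risk is confined to patients who first became positive in follow-up. This should be fixed; confidence is medium because the intended reading is not stated.

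**What to change.** - Reword the criterion so that a first-visit ANCA result is sufficient and no follow-up result is needed for inclusion. Follow-up ANCA can still be described.
- State one time origin for the Kaplan-Meier, log-rank and Cox analyses.
- Re-query the records for patients left out solely for want of a follow-up ANCA result. Restore them where the consent rules allow, and report their number by group and vital status, or state that there were none.
- If patients first positive during follow-up are included, enter them at the date of first positivity or report them separately.
- If excluded patients cannot be recovered, describe the rule as it was applied, use delayed entry at each patient's qualifying test, and label the results as conditional on reaching that test.

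The cost is one reworded criterion, one sentence on time origin and one re-query of existing records. The number to restore is unknown; across the fixed test times illustrated it runs from 0.4% (S5 = 80%, 1 month) to 12.9% (S5 = 50%, 12 months) of the cohort. Three limits remain. The timing of consent is not stated, so some early deaths may not be restorable. The document does not say when group membership is fixed. Support for delayed entry in the named software should be checked before relying on it.

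### The plan names the Student t test for two groups formed by diagnosis and has no rule for unequal variances; naming Welch's test is a cheap, minor improvement

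*Combined protocol and SAP*

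**What the plan says.** The Statistical Analysis Plan sorts continuous variables by distribution. For those judged normal, "Student t test is used for comparisons". For the others, "the Mann-Whitney U test is used for comparisons". On the level, "values are two-sided" and a P value below "0.05 is considered statistically significant". It mentions no variance check, no Welch test and no other unequal-variance version.

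Under Group Information the two groups are set by diagnosis. For MPA-ILD, "those who were diagnosed with MPA according to 2012 Chapel Hill consensus criteria are defined as" that group. The second group is what remains: "patients with isolated ANCA-positivity who did not fulfill the MPA criteria are classified as" ANCA-IIP. Under Background and Objectives, part of the purpose is to "assess the difference between microscopic polyangiitis (MPA) associated ILD and isolated ANCA-positive IIP".

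No sample size, group size, SD or list of variables expected to be normal is given.

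**The concern.** The pooled t test estimates one common variance. When the group variances differ, the pooled estimate is dominated by the larger group, and its standard error is wrong unless the group sizes are equal. If the smaller group has the larger SD, the standard error is too small and false positives exceed 5%. If the larger group has the larger SD, the standard error is too large, the test is conservative and power is lost.

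A randomised 1:1 trial is largely protected by its equal group sizes. This study is observational and has no allocation ratio. One group meets a set of criteria and the other is defined by not meeting them, so nothing in the design makes either sizes or spreads alike. At stake are the P values for variables such as age or lung function, if judged normal, in a comparison that belongs to the stated purpose.

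**Working it through.** **Inputs from the documents.** Two-sided level 0.05 and Student t test (Statistical Analysis Plan); groups defined by diagnosis (Group Information). There is no design figure to reproduce.

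**Assumptions.** Group sizes 50/50, 60/40, 60/30 and 90/30, with smaller groups used to examine cost. SD ratios from 1 to 2, in both directions. Data normal, with equal means when the error rate is calculated.

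**Large-sample formula.** For sizes n1, n2 and SDs s1, s2, the squared ratio of the pooled standard error to the true one is approximately

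r² = (s1²/n2 + s2²/n1) / (s1²/n1 + s2²/n2),

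and the actual level is 2 × [1 − Φ(1.96 r)].

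- Equal sizes or equal SDs: numerator and denominator coincide, r = 1, and the level is 5%. Both inequalities are therefore needed.
- n1 = 60, s1 = 1; n2 = 30, s2 = 1.5 (smaller group more variable): r² = (1/30 + 2.25/60) / (1/60 + 2.25/30) = 0.0708/0.0917 = 0.773; r = 0.879; level = 2 × [1 − Φ(1.723)] = 8.5%.
- Same sizes, s1 = 1.5, s2 = 1 (larger group more variable): r² = 0.0917/0.0708 = 1.294; r = 1.138; level = 2 × [1 − Φ(2.230)] = 2.6%.

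The formula depends only on the ratio of sizes and the ratio of SDs, so recruiting more patients does not cure the problem. Simulation confirms this: 150/50 and 30/10 both give 10.7% at SD ratio 1.5 with the smaller group more variable.

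**Simulated type I error of the Student test** (200,000 pairs of samples per scenario; repeat runs agree to about 0.1 point):

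| Sizes | More variable group | SD ratio 1.25 | 1.5 | 2 |
|---|---|---|---|---|
| 60/40 | smaller | 6.0% | 7.0% | 8.4% |
| 60/30 | smaller | 6.8% | 8.6% | 11.0% |
| 90/30 | smaller | 7.8% | 10.7% | 15.0% |
| 60/40 | larger | 4.1% | 3.5% | 2.8% |
| 60/30 | larger | 3.6% | 2.6% | 1.7% |
| 90/30 | larger | 2.9% | 1.8% | 0.8% |

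Welch's test, with Satterthwaite degrees of freedom, gives 4.9% to 5.1% in every row. At 50/50, or with equal SDs, the Student test gives 5.0% to 5.1%.

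**Power lost by the Student test when the larger group is the more variable.** With the mean difference set so that Welch has 80% power, Student has 76%, 72% and 65% at 60/30 (SD ratios 1.25, 1.5, 2), and 66% and 55% at 90/30 (ratios 1.5, 2).

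**Power lost by Welch when variances are in fact equal.** Starting from 80% with Student, the loss in percentage points is 0.1 at 60/40, 0.5 at 60/30, 1.0 at 90/30, 1.9 at 80/20, 3.5 at 48/12 and 11.2 at 20/5. At 20/5 Welch's own type I error is 5.0% to 5.8%.

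**The case against.** The strongest reply is that no harm is shown. It would take a variable classed as normal, unequal sizes and unequal variances together, and the documents establish none of these. The 15.0% figure needs a 3:1 split and a twofold SD ratio in the unfavourable direction; at 60/40 with ratio 1.25 the level is 6.0% or 4.1%. All of that stands, and it is why the point carries the lowest weight.

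The wording may also be loose, covering either version of the t test. That is possible, but the plan would then not say which version is used or how it is chosen, and the same edit settles it.

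The affected comparisons are descriptive. Death and lung transplantation are the defined outcomes, survival is analysed by log-rank test and Cox models, and no multiplicity adjustment is stated for the many baseline items. This stands as a limit on the consequences.

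The remedy is partial. The Mann-Whitney test falls outside this change, but it is not immune to unequal spread: for normal data with equal means and the smaller group more variable, it rejects about 7.2% and 8.7% of the time at 60/30, and 7.8% and 9.7% at 90/30 (SD ratios 1.5 and 2). That is a fair caution and does not weaken the case for Welch where a t test is used.

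Finally, the document is dated 2020-6-20 and follow-up ended in April 2019, so a change of test comes after follow-up closed. This bears on how the change is reported, not on which test is sounder.

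**Conclusion.** The concern holds as a conditional, minor point. The plan's t test relies on an equal-variance assumption that nothing in the design protects. Over assumed size ratios from 1.5:1 to 3:1 and SD ratios from 1.25 to 2, the actual level of a nominal 5% test runs from 6.0% to 15.0% when the smaller group is the more variable, and from 4.1% down to 0.8% when the larger group is. Welch's test stays at about 5% throughout.

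These figures show a possible distortion, not one known to have occurred. They rest on the plain reading of the test's name and apply only to variables treated as normal. The categorical and survival analyses are not touched.

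**What to change.** In the Statistical Analysis Plan, replace the Student t test with the Welch (unequal-variance) t test for between-group comparisons of normally distributed variables. Report the mean difference with its 95% confidence interval from the same test. The interval is a reporting addition, not needed to correct the level, but it serves the aim of assessing the difference better than a P value alone.

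The cost is a wording change and one extra output, using data already collected. The power given up if variances are equal is 1.0 point or less at 60/40, 60/30 and 90/30. If one group turns out to have only about 5 patients, the cost is real and should be acknowledged. Because follow-up has already closed, date the change and state whether it was made before the group comparisons were seen.

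### Does one unadjusted 0.05 threshold across some 24 baseline headings, with no comparison ranked as main, call for a change to the plan?

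*Combined protocol and SAP*

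**What the plan says.** The Background and Objectives section sets two aims: to describe the clinical features and long-term outcome of ANCA-positive ILD, and to assess how MPA-associated ILD differs from isolated ANCA-positive IIP. Under Group Information the population is split "In all the patients with ANCA-positive ILD": "those who were diagnosed with MPA according to 2012 Chapel Hill consensus criteria are defined as" the MPA-ILD group, and ANCA-positive patients who do not meet the MPA criteria form the ANCA-IIP group. The criteria set is named, but the collected items used to apply it are not.

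Data collection lists the baseline items to be analysed and adds that "MPO-ANCA and PR3-ANCA titers were measured by ELISA". The text on HRCT names eight signs and leaves the list open. On outcomes, the document says: "The follow-up period ended in April 2019 and the outcomes were defined as death from all causes and lung transplantation".

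The Statistical Analysis Plan gives the t test or Mann-Whitney test for continuous variables. For categorical variables, chi-square or Fisher's "exact test is used for comparisons". It continues: "Survival analysis is performed by Kaplan-Meier analysis using log-rank test", and "Cox models are used to examine the association between baseline characteristics and mortality". One rule covers all of these: a two-sided P below "0.05 is considered statistically significant". No test is called primary, secondary, exploratory or descriptive, and no adjustment is mentioned.

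**The concern.** Two things look wrong. First, when many items are each tested at 0.05 and any P value below that is called significant, some chance differences are likely to be reported as findings. The stated aim is the difference between the two groups, so a spurious baseline difference would bear directly on the study's message. The Cox associations fall under the same rule and their number is not given.

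Second, both groups share ILD and ANCA positivity, so the MPA label must rest on other features. If any of these are among the listed baseline items, a difference on them may partly reflect how the groups were formed. The plan does not mark such items, so a reader could not separate a chance difference, a built-in difference and an informative one.

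**Working it through.** The plan states no sample size, event count, power or family-wise error rate, so there is no figure of its own to reproduce.

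**Count of headings** (Data collection and the HRCT text):

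| Heading | Count |
|---|---|
| Age, gender | 2 |
| Clinical course | 1 |
| Symptoms and signs | 1 |
| Blood, urine, liver, renal, ESR, CRP | 6 |
| Rheumatoid factor | 1 |
| ANA, anti-ENA, ANCA, anti-CCP | 4 |
| Ventilation, diffusion | 2 |
| Named HRCT signs | 8 |
| Total | 25 |

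ANCA positivity is common to both groups, which leaves 25 − 1 = 24. This counts headings, not tests. Several headings are panels, the HRCT list is open, and the plan does not say which variables will be compared.

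**All 24 null, each tested once at exact size 0.05.**
- Expected false positives: 24 × 0.05 = 1.20. This does not need independence.
- Chance of at least one, independent tests: 1 − 0.95^24 = 0.708.
- With equicorrelated normal test statistics (numerical integration), the chance is 0.690, 0.595, 0.458 and 0.311 at correlations of 0.1, 0.3, 0.5 and 0.7.

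**Other assumptions move the answer.**
- Only 12 of the 24 null: 12 × 0.05 = 0.60 expected; 1 − 0.95^12 = 0.460 if independent, 0.232 at correlation 0.7.
- MPO-ANCA and PR3-ANCA titers added, 26 nulls: 26 × 0.05 = 1.30 expected; 1 − 0.95^26 = 0.736 if independent, 0.321 at correlation 0.7.
- Gender and the eight HRCT signs tested by Fisher's exact test, which is conservative. With an assumed 30 to 50 patients per group and prevalence of 5% to 40%, its size runs from 0.0015 to about 0.032. Expected: 15 × 0.05 + 9 × 0.0015 = 0.76, up to 15 × 0.05 + 9 × 0.032 = 1.04. Chance of at least one: 0.543 to 0.654 if independent, 0.257 to 0.283 at correlation 0.7.
- Rheumatoid factor, ANA, anti-ENA and anti-CCP also handled as positive or negative by Fisher at the smallest size: 11 × 0.05 + 13 × 0.0015 = 0.57 expected; 1 − 0.95^11 × 0.9985^13 = 0.44 if independent.

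Across these scenarios the chance of at least one false positive runs from 23% to 74%. The direction is clear, but the documents do not fix where in that range this study sits.

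**Effect of naming a main comparison now.** A single comparison chosen in advance and tested at two-sided 0.05 would have a type I error of 0.05. The document is dated 2020-6-20 and follow-up ended in April 2019, about 14 months before. Unless an earlier record exists, the choice could not be presented as made in advance, so that 0.05 could not be claimed.

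**Items used to assign MPA.** The document cites the criteria by name and does not reproduce them. It therefore cannot be shown from the text that any listed item decided membership. An item that was only one of several routes to the diagnosis need not differ between the groups in a given sample.

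**The case for a change.** The strongest case for a change is that the plan does more than describe: it declares significance. Nothing warns the reader that many comparisons share one threshold, and even the lowest scenario above leaves a 23% chance of at least one false claim. The remedy would be wording only: estimates with 95% confidence intervals, an exploratory label, and a note on items used to assign MPA. It would need no new data and no formal adjustment.

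Much of this stands. The absences are real, the count and the arithmetic are right, and the heading count probably understates the number of tests. What does not stand is the step to a required change. Unadjusted P values in a two-group baseline table are common in descriptive observational work, and nothing in the document presents them as confirmatory. The 71% figure needs every heading to be null, which sits badly with the argument that some items differ because of how the groups were formed. The comparison of interest is also less open than it seems: the two groups are named in the objective, the outcomes are defined and a log-rank test is specified. Only a formal ranking is missing. Whether death and transplantation are combined is a separate question.

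**Conclusion.** No change to the plan follows. The gap is an unwritten reporting convention in a descriptive study, and analysts can fill it sensibly by giving intervals beside the P values, reading the baseline and Cox results as exploratory, and saying where a variable contributed to the MPA diagnosis. None of this alters a test, an estimate or a result. Dropping the word significant from comparisons that are the study's stated aim is a preference on which reasonable statisticians differ, and ranking the comparisons after follow-up has ended brings no gain in error control.

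The size is 1.2 expected false positives if all 24 headings are null, with a chance of at least one of 71% under independence and 31% at correlation 0.7. Those figures rest on one test per heading at exact size 0.05. The wider range of 23% to 74% rests on assumed null counts, correlations, group sizes and prevalences. The view would differ if the study claimed a controlled overall error rate or tied a decision to one of these P values; the document does neither.
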